7 CLINICAL EVALUATIONS AND PROCEDURES

7.1 Table 1: Schedule and Sequence of Data Collection

Assessment Schedule

	Screening	Baseline/ Randomization		M1 +/- 7 days		M2 +/- 7 days		End of Treatment/M3 +/- 7 days	7 Day Follow Up
		W1	W3	W4	W7	W8	W11	W12	
Informed Consent	X								
Concomitant Medications	X	X		X		X		X	X
Relevant Medical History/Current Medical Condition	X								
Mini-Mental Status Exam, 2 nd Edition (MMSE)	X								
Self-Reported Cognitive	X								

Impairment Since Chemotherapy									
Wechsler Test of Adult Reading (WTAR)		X							
Hopkins Verbal Learning Test, Revised (HVLТ-R): Form 1		X							
Hopkins Verbal Learning Test, Revised (HVLТ-R): Form 2							X		
Controlled Oral Word Association Test (COWA): T1		X							
Controlled Oral Word Association Test (COWA): T2							X		
Color Trails – Part 1 (Form A)		X					X		
Color Trails – Part 2 (Form A)		X					X		
Brief Visuospatial Memory Test – Revised (BVMT-R): Form 1		X							
Brief Visuospatial Memory Test – Revised (BVMT-R): Form 2							X		
Digit Span (subset of WMS-IV)		X					X		
Symbol Digit Modalities Test (SDMT)		X					X		
Rey Complex Figure Copy (Copy Trial Only)		X					X		
Demographic Questionnaire		X							
Godin-Leisure Time Exercise Questionnaire		X					X		
Primary Care Evaluation of Mental Disorders Health Questionnaire (PHQ-9)		X					X		
Fatigue Symptom Inventory (FSI)		X					X		
Patient’s Assessment of Own Functioning Inventory (PAOFI)		X					X		
MRI-Resting state functional MRI and structural MRI.		X					X		
Anthropometric Measurements ¹		X					X		
ECOG	X						X		
2 Day Food Record ²		X		X		X	X		
Hematology (CBC) ³	X			X		X	X		
Blood Chemistry (CMP, PT/PTT, LDL) ⁴	X			X		X	X		

Research Labs (Oxidative stress, Cytokine)	X							X	
Adverse Events				X		X		X	X
Limited Physical Exam	X ⁵							X	
Study Agent/Multivitamin Distribution		X		X		X			
Study Agent Intake & Symptom Logs		X		X		X		X	
Pill Counts				X		X		X	
Follow Up Phone Call									X

¹ Height, Weight, BMI, Waist, & Hip Circumference

² Dietary recall forms and instructions will be distributed in person at the screening visit and collected at the baseline, week 4, week 8, and end of treatment visits

³ Hematology labs do not need to be performed at screening visit if lab results are available within the previous 28 days (+/- 3 days)

⁴ Blood Chemistry labs do not need to be performed at screening visit if lab results are available within the previous 28 days (+/- 3 days)

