7.7.5 Functional markers (Eastern Cooperative Oncology Group: ECOG)¹¹⁰ (Appendix VI): Functional Markers allow subjects to be monitored for basic functional status and to monitor any functional impairment. Limitations in the activities of daily living have been identified secondary to fatigue and lethargy reported by this patient population. (Screening & 3 months)

7.7.6 Participants will also be provided with **Study Agent Intake and Symptom log** (Appendix VII) which they will be required to complete daily. Study agents and instructions for administration will be distributed to subjects at baseline and monthly during scheduled visits. Each batch will contain a supply for approximately 1 month. The study intake log will require the subject to check that study agent has been taken and will be secured to the symptom monitoring scale to ease completion and to remind patients to monitor symptoms.

7.7.7 Pill counts will be completed at monthly visits prior to providing subject with a new batch of supplements. Working at a flat surface, the research coordinator applies a pair of latex gloves and then pours the

bottle of study agent/placebo or multivitamin on to the pill count tray. Using a gloved hand or sorter the pills are counted individually and returned to the empty bottle. In the event of discrepancy between actual and expected count, the process is repeated.

7.7.8 Adverse events monitoring (Appendix VIII):

All adverse events (AEs) that are reported by the subject, detected during a visit, physical examination, or laboratory work-up will be recorded in the participant's study record and recorded on the CRF. All AEs that occur after the start of the study agent will be recorded on the AE CRF whether or not related to study agent. The following information will be captured for each AE: date reported; verbatim term; CTCAE Term (v 4.0); onset and resolution date; severity grade; attribution to study agent; whether or not the event was reported as an SAE; action taken; whether or not the subject dropped due to the AE; outcome; and comments.

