8.1 Primary Endpoint

The primary efficacy endpoint is to generate effect sizes for changes in the number of impaired neuropsychological tests. The planned intervention period is three months. Neuropsychological outcomes will be examined using a 2 (group; COGNUTRIN, placebo) X 2 (time; baseline, three-months) repeated measures ANOVA to examine differences in the number of impaired neuropsychological tests. Age, premorbid cognitive functioning, depression and fatigue will be evaluated for association with neurocognitive performance and entered as covariates in statistical analyses if a marginally significant association ($p < .10$) is observed.

The primary safety endpoint is incidence and severity of AEs occurring during intervention with either COGNUTRIN or placebo. All AEs that are reported by the subject, detected during a visit, physical examination, or laboratory work-up will be recorded in the participant's medical record and recorded on the CRF. All AEs that occur after the informed consent is signed will be recorded on the AE CRF whether or not related to study agent.

The sample size proposed in the current protocol will not provide sufficient statistical power, but information regarding effect sizes will be gathered and used as motivation for future clinical trials. We estimate that a minimum evidence of improvement in cognitive function with the 3 month intervention as indicated by a score of 1 standard deviation or more above population norms on the Hopkins Verbal Learning Test – Revised, Controlled Oral Word Association Test, or Color Trails Test Part 1 or 2 will be considered adequate to justify progression to a larger study.

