10.1 Adverse Events

10.1.1 Reportable AEs

All AEs that are reported by the subject, detected during a visit, physical examination, or laboratory work-up must be recorded in the participant's medical record and recorded on the CRF. All AEs that occur after the start of study agent must be recorded on the AE CRF whether or not related to study agent.

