12.6 Evaluation of Toxicity

The primary safety endpoint is incidence and severity of AEs occurring during intervention with either COGNUTRIN or placebo. All participants will be evaluated for toxicity from the time that the informed consent is signed up to the end of the intervention according to the NCI CTCAE version 4.0. Standard assessment of toxicity will also include interviews, clinical evaluation, and monitoring of laboratory values. All toxicity data will be summarized by category and grade in a standard fashion. Proportions experiencing most common types of toxicity in this trial will be estimated and exact 95% CIs calculated based on the exact binomial distribution for these proportions will be reported. Compliance will be evaluated by standard pill counts, diet records and plasma levels of anthocyanins and erythrocyte n-3 index. Any unusual patterns in compliance will be noted and apparent discrepancies between pill counts or diet records and plasma levels by will be summarized as well.

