7.7.8 Adverse events monitoring (Appendix VIII)

- Added the following:
For each subject, AE’s will be collected at the screening, Month 1, Month 2, Month 3/EOT, visits as well as at the 7-day post-treatment follow-up call by the clinical research coordinator. AE’s collected at the screening visit will be catalogued as baseline symptoms by the clinical research coordinator and the AE log will be reviewed and signed by either the patient’s medical oncologist or PI. AE’s collected during Month 1 and 2 visits will be reviewed with the patient by the nurse who drew their blood at CRU and the AE log will be signed by the principal investigator. Finally, at the Month 3 visit, the participant’s medical oncologist will review the AE log with the patient and sign-off on the reported symptoms; if the medical oncologist is unavailable to sign the AE log at this visit, then the PI will review and sign the form. AE’s reported at the 7-day follow-up call will be reviewed and signed by the PI. The participant’s reported symptoms at this time point will be documented on a powerchart telephone note by the clinical research coordinator. Serious adverse events (SAE’s) are reported to IRB and FDA. If a participant reports an SAE, the PI will immediately be informed and she will then report it to the IRB and FDA. AE logs will be scanned to patients’ medical records by the clinical research coordinator once they are off-study.

MCC# 17089

Amendment 9.0; 22 January 2015

Pilot Trial of COGNUTRIN in Breast Cancer Survivors

Principal Investigator: [name], RD, FADA

Summary of Changes:

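### Section 12.6 counts toxicity from consent and gives the baseline symptom log no role, so symptoms present before the first dose may enter the primary safety endpoint

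*Combined protocol and SAP*

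**What the plan says.** The endpoint is stated in section 8.1, and again in 12.6: "The primary safety endpoint is incidence and severity of AEs occurring during intervention with either COGNUTRIN or placebo".

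The analysis is in section 12.6. Its window is wider than that endpoint: "All participants will be evaluated for toxicity from the time that the informed consent is signed up to the end of the intervention". The summary rule is "All toxicity data will be summarized by category and grade in a standard fashion". For the most common types of toxicity, "exact 95% CIs calculated based on the exact binomial distribution for these proportions will be reported". Section 12.6 mentions neither the baseline log, nor treatment-emergent events, nor change from baseline grade. It does not say whether the proportions are by arm or pooled.

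The baseline log is in section 7.7.8, where AEs are "collected at the screening visit will be catalogued as baseline symptoms by the clinical research coordinator". No analysis section refers to that catalogue.

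The start of AE recording is stated in two ways:

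- Section 7.7.8: "All AEs that occur after the start of the study agent will be recorded on the AE CRF whether or not related to study agent".
- Section 10.1.1: "All AEs that occur after the start of study agent must be recorded on the AE CRF whether or not related to study agent".
- Section 8.1, by contrast, starts the same form when consent is signed.

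In Table 1 (section 7.1), the row "Adverse Events" is marked at months 1, 2 and 3 and at the 7-day call. It is not marked at screening, although 7.7.8 collects AEs there.

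**The concern.** The women have finished anthracycline and/or taxane treatment within the past 6 months, with or without radiation, and may be on endocrine therapy (section 4.1). Section 7.7.5 says that fatigue and lethargy are reported in this population. Some symptoms at entry are therefore to be expected.

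Screening procedures follow consent (section 7.2.1), so a symptom logged at screening lies inside the window that 12.6 sets. If it is counted, the result mixes incidence on treatment with prevalence at entry. The types that turn out most common, and so receive confidence intervals, may then be types that were common before dosing. A symptom that worsens on the agent also has no stated way to be counted as worse.

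This matters because safety is a primary endpoint and section 6.5 promises a formal comparison of safety between the arms. Section 10.1.4 adds to the difficulty: an AE is treated as due to drug unless it is clearly unrelated, so attribution will not reliably remove a carried-over symptom.

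**Working it through.** The plan states no rate, sample size or power for the safety endpoint, so there is no figure of its own to reproduce. The check has two parts.

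**1. Which events enter the count**

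| Section | Starts at | Screening symptom included? |
|---|---|---|
| 7.7.8, AE form | first dose | no, if onset decides |
| 10.1.1, AE form | first dose | no, if onset decides |
| 8.1, AE form | consent | yes |
| 8.1 and 12.6, endpoint sentence | during intervention | no, if onset decides |
| 12.6, evaluation window | consent | yes |

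The text supports two different counts of one endpoint. Choosing the first dose as the start settles symptoms that ended before dosing. It does not fully settle one that persists and is reported again on the daily symptom log or at a monthly interview. Onset date and grade are recorded for each AE (7.7.8, 10.1.2), but no rule says that an earlier onset excludes the event or that a rise in grade makes it count.

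**2. What counting carry-over would do**

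Inputs: 20 women per arm (section 12.4). Everything else is assumed. Let *b* be the share who already have the symptom, equal in both arms and always recounted, and *p* the probability of a new event among the rest. The observed proportion is

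b + (1 − b)p,

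and the difference between arms is

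(1 − b)(p_active − p_placebo).

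The factor (1 − b) is algebra and does not depend on the rates chosen. For illustration, take p_active = 0.45 and p_placebo = 0.10:

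| b | Active | Placebo | Difference | Fisher power (two-sided 0.05) |
|---|---|---|---|---|
| 0 | 0.45 | 0.10 | 0.35 | 0.62 |
| 0.2 | 0.2 + 0.8×0.45 = 0.56 | 0.2 + 0.8×0.10 = 0.28 | 0.28 | 0.31 |
| 0.4 | 0.4 + 0.6×0.45 = 0.67 | 0.4 + 0.6×0.10 = 0.46 | 0.21 | 0.17 |
| 0.6 | 0.6 + 0.4×0.45 = 0.78 | 0.6 + 0.4×0.10 = 0.64 | 0.14 | 0.10 |

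With 0.40 against 0.10 the pattern is the same: Fisher power is 0.49, 0.24, 0.12 and 0.08.

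For a single arm, the Clopper-Pearson 95% limits are the 2.5% point of Beta(x, n − x + 1) and the 97.5% point of Beta(x + 1, n − x):

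- 2 new events in 20: 10%, interval 1% to 32%.
- The same 2 plus 8 women with a carried-over symptom, 10 in 20: 50%, interval 27% to 73%.

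A count of new or worsened events recovers the full difference only if women with the symptom at entry worsen at the rates at which others develop it. If they never worsen, the treatment-emergent proportions are (1 − b)p. At b = 0.4 that is 0.27 against 0.06: still a difference of 0.21, but a ratio of 0.27/0.06 = 4.5 instead of 0.67/0.46 = 1.5, and proportions that describe incidence.

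**The case against.** The strongest reply is that the documents already point to separating the two. Screening AEs are labelled baseline symptoms, two sections start the AE form at the first dose, the endpoint sentence says during intervention, and onset dates are captured. On that reading an analyst would leave pre-dose symptoms out. This stands as evidence of intent, and it rules out the stronger inference that carried-over symptoms do count as toxicity and mask effects of the agent. The text is contradictory on the start point and silent on persisting symptoms; it does not direct that they be counted.

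A reader might also infer from Table 1 that nothing about symptoms is recorded before dosing. That is not so. Current medical condition and a limited physical exam are taken at or before baseline (7.2.3, 7.2.4), the fatigue and depression questionnaires are completed at baseline (7.3.4), and 7.7.8 itself collects AEs at screening. Fatigue is also analyzed separately as a change under treatment (12.5.4). What is missing is a rule connecting these records to 12.6.

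The illustration has limits too. Its rates are chosen, section 12.6 plans estimation rather than a test, and the trial does not claim adequate power. With no carry-over at all, Fisher power at 20 per arm is only 24% for 30% against 10%, and 7% for 20% against 10%, so sample size is the larger constraint on any test. Randomization makes carry-over comparable between arms on average, so no bias toward one arm follows. It does not turn a mixed proportion into an incidence or restore the lost contrast.

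**Conclusion.** The point holds in conditional form. Sections 8.1 and 12.6 conflict with 7.7.8 and 10.1.1 on when counting starts, and 12.6 gives no role to the baseline log. Followed literally, 12.6 may count pre-dose symptoms in a primary endpoint. This would raise the proportions and move their exact intervals upward, and under equal, fully recounted carry-over it would reduce any arm difference by the factor (1 − b). The value of b is unknown because the documents give no background rate, so the power figures are illustration only. The gap is worth closing before the safety data are tabulated, because two analysts following different sections could report different incidences from the same records.

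**What to change.** 1. State one start point for AE counting and use it in 7.7.8, 8.1, 10.1.1 and 12.6.
2. In 12.6, count a woman as having a given toxicity only if its CTCAE grade after the first dose is new or higher than on her baseline symptom log.
3. Report baseline grade against worst on-treatment grade, by arm, and compute the exact 95% intervals by arm on these treatment-emergent proportions.
4. Mark the screening symptom record in the Adverse Events row of Table 1, to match 7.7.8.

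The log is already collected and grade is already a data element, so the cost is wording, one mark in Table 1 and minor extra tabulation. The rule depends on the baseline log carrying CTCAE grades; 7.7.8 should say so explicitly.

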4.2 Criteria for exclusion will include: 1) Use of estrogens (oral, dermal or vaginal), progesterone (oral or topical), or androgens during the previous 3 months, 2) Use of over the counter steroid hormonal supplements 3) Patients with advanced or Stage IIIC or IV breast cancer or other cancers. 4) Use of n-3 fatty acids or high dose antioxidant supplements other than what is provided in the trial. 5) History of known allergy to components of the study supplements. 6) Subjects with renal or liver disease (AST/ALT $>$ 5.0 x upper limit of normal as evidenced by impairment of baseline laboratory values); Actual creatinine clearance of $<$ 60 utilizing the Cockcroft-Gault formula (1976), which employs creatinine measurements and a patient's weight to predict the clearance. (The constant for women is 1.04). 7) Concurrent participation in another chemoprevention trial. 8) Evidence of bleeding diathesis or coagulopathy (PTT and/or either PT or INR $>$ 1.5x upper limit of normal (except for subjects receiving anti-coagulation therapy). Concurrent use of Coumadin or Warfarin will be acceptable and monitoring patients on warfarin or Coumadin will follow the standard of care as dictated by the prescribing physician (PT/PTT). If the prescribing physician is not a Moffitt MD, then the prescribing MD

will be notified by the research staff of the subject participating in the study, and monitors for PT, PTT will be obtained from patient during the 3 month study visit for review. 9) Subjects with metabolic abnormalities (e.g. thyroid disorders, insulin dependent diabetes, rheumatologic disease etc.). Subjects with metabolic disorders (a) who are otherwise eligible, (b) treated for hypothyroidism by their primary MD with Synthroid (levothyroxine) and (c) with the approval of the Moffitt treating oncologist will not be excluded from the study. 10) Patients with known claustrophobia, presence of pacemaker and/or ferromagnetic material in their body that would prohibit MRI imaging (ex. tissue expanders). 11) Medical history of concussions 12) Other acute or chronic medical or psychiatric condition or laboratory abnormality that may increase risk associated with study participation or study drug administration, or may interfere with interpretation of study results, and in the judgment of the investigator would make the subject inappropriate for entry into this study.

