eicosapentaenoic acid (EPA) and docosahexaenoic acid (DHA) ethyl esters. Lovaza® is provided by GlaxoSmithKline, who has authorized the FDA center for Drug Evaluation and Research, Division of Metabolic and Endocrine Drug Products to reference Lovaza® Capsules IND # 45,998. Bottles are labeled to comply with study requirements and applicable regulations for investigational drug use. Bottles with study agent will be stored at controlled room temperature (15-30 °C). The products are both standardized and examined for content, stability and bioavailability and the study will be conducted with an investigator-initiated new drug (IND) approval from the Food and Drug Administration (FDA) as mandated by the National Cancer Institute for Phase I-III clinical trials. Use of n-3 fatty acids may decrease platelet aggregation and subjects with evidence of bleeding diathesis or coagulopathy will not be included in this study and those with concurrent use of Coumadin or warfarin will be observed closely. The follow-up monitoring for PT, PTT for patients on warfarin and/or Coumadin will follow the standard of care as dictated by the prescribing physician. The prescribing MD will be notified by the research staff of the subject participating in the study, and monitors for PT, PTT will be obtained from patients during the monthly clinic visits.

5.2 Rationale for Dose selection and Administration:

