Adverse events requiring delays or permanent discontinuation of Cognutrin® are listed in the table below:

Event	Action
Grade 1 & 2 constitutional, dermatological, gastrointestinal (GI), metabolic and pain symptoms Examples: Rash Allergic rhinitis, cough, bronchitis. Abdominal Pain Belching/Gas Nausea/Vomiting Diarrhea	No Action Required Inform MD Document event in research and medical record
Grade 3	Discontinue Cognutrin ®/Notify Study PI
Grade 4	Discontinue Cognutrin ®/Notify Study PI
Grade 2, 3, or 4 abnormal liver function tests ^{1,2} as determined by NCI CTC version 4.0	Discontinue Cognutrin ®/Notify Study PI and Monitor until it returns to normal

1. Tests used to monitor liver function include: albumin, total and direct bilirubin, alkaline phosphatase, AST, ALT, total protein, PT/PTT.)
2. In the event that PT/PTT is abnormal due to anticoagulant therapy, treatment and/or drug discontinuation will be at the discretion of the site investigator/MD.

Regardless of the reason for holding study drug treatment, the maximum allowable length of treatment interruption is 1 week. Interruption of intake of >1 week will result in discontinuance of subject from the study. Patients who have an ongoing Cognutrin ®-related Grade 3-4 or serious adverse event at the time of discontinuation from study treatment will continue to be followed until resolution of the event or until the event is considered irreversible by the study MDs.

In addition, a standard multivitamin/ mineral preparation will be provided free of charge during the study duration, to assure a consistent baseline intake of essential vitamins and minerals among all study participants during the study period and to encourage subjects from not using other supplements that may contain components of the study agents. Subjects in the treatment and placebo arms will be provided these multivitamin/mineral supplements and instructed to consume 1 tablet daily with the dinner meal.

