7.4 Evaluations during Study Intervention

- 7.4.1 **Weeks 3, 7, 11:** Participants will be contacted reminding them to complete diet survey and to bring completed survey, study agent /symptom logs and all left over study agent (including multivitamin) to their next in person visit scheduled.
- 7.4.2 **Weeks 4 & 8 (+/- 7 days):** Participants will come in person monthly for the following:
 - 7.4.2.1 Review of completed diet surveys, study agent/symptom logs, adverse events and concomitant medications by CRC and verified with CRU RN.
 - 7.4.2.2 Collection of any unused nutritional supplement/ placebo and multivitamin for pill counts
 - 7.4.2.3 Safety labs (CBC, CMP, PT/PTT, and LDL) will be drawn
 - 7.4.2.4 Participant will be supplied with a new one-month supply of nutritional supplement or placebo

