10.1.3 Severity of AEs

Identify the AE using the NCI Common Terminology Criteria for AEs (CTCAE) version 4.0. The

CTCAE provides descriptive terminology and a grading scale for each AE listed. A copy of the CTCAE can be found at http://evs.nci.nih.gov/ftp1/CTCAE/CTCAE_4.03_2010-06-14_QuickReference_8.5x11.pdf

AEs will be assessed according to the CTCAE grade associated with the AE term. AEs that do not have a corresponding CTCAE term will be assessed according to their impact on the participant's ability to perform daily activities as follows:

Grade	Severity	Description
1	Mild	Asymptomatic or mild symptoms, clinical or diagnostic observations only; intervention not indicated
2	Moderate	Minimal, local or noninvasive intervention indicated; limited age-appropriate instrumental ADL*
3	Severe	Severe or medically significant but not immediately life-threatening; hospitalization or prolongation of hospitalization indicated; disabling; limiting self care ADL**
4	Life threatening	Life threatening consequences; urgent intervention indicated
5	Fatal	Death related to AE

* Instrumental ADL refer to preparing meals, shopping for groceries or clothes, using telephone, managing money, etc.

** Self care ADL refer to bathing, dressing and undressing, feeding self, using the toilet, taking medications, and not bedridden.

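### Section 12.6 analyses the safety laboratory values only as CTCAE categories and grades, so a systematic shift in clotting, platelets, LDL or chemistry, or any change inside the reference range, is not estimated

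*Combined protocol and SAP*

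**What the plan says.** - **What is measured.** Table 1 (section 7.1) has a CBC row and a row for "Blood Chemistry (CMP, PT/PTT, LDL", both marked at screening and at weeks 4, 8 and 12. Section 7.4.2.3 agrees for weeks 4 and 8: "Safety labs (CBC, CMP, PT/PTT, and LDL) will be drawn". Section 7.7.11 files these tests under safety markers, and the CBC panel described there includes the platelet count. The schema lists LDL at screening and week 12 but not at weeks 4 and 8.
- **How it is analysed.** Section 12.6 grades toxicity by CTCAE v4.0, mentions that laboratory values are monitored, and then states: "All toxicity data will be summarized by category and grade in a standard fashion". It adds exact binomial 95% intervals for the proportions with the most common toxicities. It names no mean, change from screening, shift table or between-arm difference for any laboratory test.
- **What the protocol says about safety aims.** Section 6.5 promises a formal comparison of safety between the arms, but section 12 gives no method for it. Sections 8.1 and 12.4 say the pilot is meant to supply effect sizes for later trials.
- **Why clotting is of interest.** Section 5.1.2: "Use of n-3 fatty acids may decrease platelet aggregation". Section 4.2, item 8: "Concurrent use of Coumadin or Warfarin will be acceptable".

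**The concern.** Each laboratory test gives a number, a pre-treatment value for the same woman, and a concurrent placebo arm. Reducing that to a grade discards the first, leaves the second unused and makes little of the third. A modest movement in PT, PTT, platelets or LDL across the whole active arm would mostly stay below the first grade boundary, so the planned table would show a few isolated abnormal values or none.

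This matters because safety is a primary endpoint and the pilot's stated purpose is to inform a larger trial. That trial's designers would want to know whether the combination moves clotting tests or lipids, in which direction, and with what uncertainty. Grade counts in about 20 women per arm do not give them that.

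PT/PTT needs extra care. Women on warfarin or Coumadin may take part, and their values reflect anticoagulant treatment as well as any agent effect. Section 12.6 does not separate them.

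**Working it through.** The plan states no figure for laboratory safety, so there is none to reproduce. The check has two parts.

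**1. Is there any analysis on the measured scale?** Sections 8.1, 8.2 and 12.1 to 12.7 were read for one. The ANOVA in 8.1 and 12.4 is for impaired cognitive tests. Section 12.5 covers mediation, imaging, subjective cognition, compliance, fatigue and depression. Section 12.6 is by category and grade, with proportions. None of these uses a screening laboratory value or estimates a between-arm laboratory difference.

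**2. How much does the choice of scale matter?** This is an illustration only.

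Inputs:
- n = 20 per arm (section 12.4).
- Assumed: values normal with common SD 1; upper limit at the placebo mean + 2 SD; true shift 0.8 SD in the active arm.
- Assumed: correlation r = 0.5 between screening and week 12. The plan's stability coefficient of .5 (section 12.4) is for the cognitive outcome; none is given for laboratory tests.

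Share above the limit:
- Placebo: 1 − Φ(2) = 0.023, so 20 × 0.023 ≈ 0.5 women.
- Active: 1 − Φ(2 − 0.8) = 1 − Φ(1.2) = 0.115, so 20 × 0.115 = 2.3 women.
- Chance that at least one active-arm woman is above the limit: 1 − (1 − 0.115)^20 ≈ 0.91.

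So isolated abnormal values probably would be seen. The plan's own exact intervals, if reported by arm, would say little about a difference:

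| Women above limit | Exact 95% CI |
|---|---|
| 0 of 20 | 0% to 16.8% |
| 1 of 20 | 0.1% to 24.9% |
| 2 of 20 | 1.2% to 31.7% |
| 3 of 20 | 3.2% to 37.9% |

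Counts of 0 or 1 on placebo and 2 or 3 on active are typical here, and the intervals overlap over most of their length.

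Baseline-adjusted mean difference at week 12:
- Standard error = √(2/n) × √(1 − r²) = √(2/20) × √0.75 = 0.316 × 0.866 = 0.274 SD.
- Half-width = t(0.975; 37 df) × 0.274 = 2.026 × 0.274 ≈ 0.55 SD.
- With 18 per arm (the 10% loss in section 4.3): 2.035 × √(2/18) × √0.75 = 2.035 × 0.289 ≈ 0.59 SD.
- Without any baseline adjustment (20 per arm): 2.024 × 0.316 ≈ 0.64 SD.

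An estimate of 0.8 SD would carry an interval of roughly 0.25 to 1.35 SD. If the baseline correlation were zero, it would still be about 0.16 to 1.44 SD.

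**The case against.** The declared primary safety endpoint is the incidence and severity of adverse events, and a table by category and grade matches it. This is a 40-subject feasibility pilot, the tests are run in real time for monitoring, and the plan is silent on descriptive laboratory tables rather than opposed to them. All of that stands, and it is why the point is minor. It does not supply the missing estimate.

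Stronger conclusions are tempting, but the documents do not support them:

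- *Shifts near the limits go unreported.* A reader might infer this. Section 10 counts an abnormal laboratory finding as an adverse event, and 10.1.1 requires events found in the laboratory work-up to be recorded. Values just outside the range can therefore be graded.
- *PT/PTT has a rule only as a liver test.* Footnote 1 in section 6.5 invites this: "Tests used to monitor liver function include: albumin, total and direct bilirubin, alkaline phosphatase, AST, ALT, total protein, PT/PTT". But 4.2 item 8 has a PT/PTT/INR criterion for coagulopathy, 5.1.2 follows PT/PTT in women on warfarin, and footnote 2 in 6.5 deals with anticoagulant-related abnormality.
- *An asymptomatic LDL rise can be at most grade 1.* Section 10.1.3 says "AEs that do not have a corresponding CTCAE term will be assessed according to their impact" on daily activities. Whether LDL has a CTCAE term is not shown in the documents, and the fallback grades also refer to intervention being indicated and to medical significance.
- *The trial would report that there was no toxicity.* No section plans such a statement.
- *The added tables would capture the named platelet risk.* No section says PT, PTT or platelet count measures platelet aggregation, and none names an LDL risk. These are simply the safety data the protocol chose to collect.

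Setting the power of a test on out-of-range counts against that of a test on means would also be unfair to the plan, which contains no such count test. The comparison above uses interval widths for that reason.

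**Conclusion.** The point holds, at minor severity. Repeated safety laboratory data with a screening value and a placebo arm are to be reported only as grades and proportions. What goes unestimated is the mean shift and any change inside the reference range.

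Under the illustrative assumptions, a 0.8 SD shift shows up as about 0.5 versus 2.3 women above the limit. The same data would give a mean difference with a 95% CI half-width of about 0.55 SD. The finding that no such estimate is planned needs no assumptions. The sizes depend on normality, the position of the limit, the shift and the assumed correlation. The correlation is untested for laboratory values: samples are non-fasting, and Table 1 allows screening results up to 28 days old. Smaller shifts would not be estimated precisely on either scale.

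**What to change.** Keep the grade table and exact intervals in section 12.6, and add:

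1. For PT, PTT, platelet count, LDL, AST/ALT and creatinine: values and change from screening, by arm and visit.
2. For each, the week-12 COGNUTRIN minus placebo difference from ANCOVA on the screening value, with a 95% CI, labelled descriptive and not adjusted for multiplicity.
3. PT/PTT shown separately for women on warfarin or Coumadin.

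The LDL schedule must be reconciled: the schema has no LDL at weeks 4 and 8, while Table 1 and 7.4.2.3 do. Until that is settled, the LDL comparison rests on screening and week 12, which both versions include. Table 1 and 7.7.11 also differ on how old an existing screening result may be (28 versus 7 days, each ±3). Because that result becomes the baseline value, those passages must be reconciled too.

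The cost is a few extra tables from tests already scheduled, with no new visits. The downside is several unadjusted intervals, some of which may exclude zero by chance. Nothing here alters dosing, monitoring or discontinuation rules.
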